3.7.1.4 AE summaries

The following adverse event summaries will be produced by treatment group:

- Summary of deaths and adverse events
- Adverse events, irrespective of causality, by primary system organ class, preferred term and maximum grade

- Adverse events with suspected relationship to study treatment by primary system organ class, preferred term and maximum grade
- Most common grade 3-4 adverse events, irrespective of causality, by preferred term and maximum grade (greater than x% in either arm)
- Adverse events, irrespective of causality, by primary system organ class and maximum grade
- Adverse events, irrespective of causality, by preferred term and maximum grade
- Adverse events with suspected relationship to study treatment by preferred term and maximum grade
- On treatment deaths by preferred term
- Deaths, by primary system organ class and preferred term
- Serious adverse events, irrespective of causality, by primary system organ class and preferred term and maximum grade
- Serious adverse events with suspected relationship to study treatment, by primary system organ class, preferred term and maximum grade
- Adverse events leading to study drug discontinuation, irrespective of causality, by primary system organ class, preferred term and maximum grade
- Adverse events leading to study drug reductions, irrespective of causality, by primary system organ class, preferred term and maximum grade
- Adverse events leading to study drug interruptions, irrespective of causality, by primary system organ class, preferred term and maximum grade
- Adverse events requiring additional therapy, irrespective of causality, by primary system organ class, preferred term and maximum grade
- On-treatment deaths and SAEs with fatal outcome, by SOC and PT

AEs of interest will also be summarized. See [Section 3.7.1.5](#) for the grouping details.

Subgroup analyses by endocrine combination partner subgroups (tamoxifen and goserelin; NSAID and goserelin) will be performed for the analysis of adverse events, irrespective of causality, by primary system organ class, preferred term and maximum grade.

Separate summaries will be provided for adverse events, deaths and serious adverse events occurring during the cross-over on-treatment period for the cross-over analysis set.

3.7.1.5 Grouping of adverse events of special interest

An adverse event of special interest is a grouping of adverse events that are of scientific and medical concern specific to ribociclib. These groupings are defined using MedDRA terms, SMQs (standardized MedDRA queries), HLGs (high level group terms), HLTs (high level terms) and PTs (preferred terms). Customized SMQs (Novartis MedDRA queries, NMQ) may also be used. A NMQ is a customized group of search terms which defines a medical concept for which there is no official SMQ available or the available SMQ does not completely fit the

need. It may include a combination of single terms and/or an existing SMQ, narrow or broad. For each specified AESI, the number and percentage of patients with at least one event of the AESI occurring during the double-blinded on-treatment period will be summarized.

Summaries of these AESIs will be provided by treatment arm, (specifying grade, SAE, relationship, leading to treatment discontinuation, leading to dose adjustment/interruption, etc.).

A Case Retrieval Sheet (CRS) with the exact composition of the AE groupings is to be used to map reported AEs to the AESI groupings. This file may be updated (i.e., it is a living document) based on review of accumulating trial data, and therefore the groupings are also subject to potential change. The most up-to-date version of the CRS will be used at the time of the analysis.

3.7.1.6 Clinical trial safety disclosure

For the legal requirements of ClinicalTrials.gov and EudraCT, two required tables will be provided for the safety set and the cross-over analysis set population: 1) adverse events which are not serious adverse events with an incidence greater than 5% by system organ class and preferred term and 2) serious adverse events and SAE suspected to be related to study treatment by system organ class and preferred term..

If for the same patient, several consecutive AEs (irrespective of study treatment causality, seriousness and severity) occurred with the same SOC and PT:

- a single occurrence will be counted if there is ≤ 1 day gap between the end date of the preceding AE and the start date of the consecutive AE
- more than one occurrence will be counted if there is > 1 day gap between the end date of the preceding AE and the start date of the consecutive AE

For occurrence, the presence of at least one SAE / SAE suspected to be related to study treatment / non-SAE has to be checked in a block e.g., among AE's in a ≤ 1 day gap block, if at least one SAE is occurring, then one occurrence is calculated for that SAE.

The number of deaths resulting from SAEs suspected to be related to study treatment and SAEs irrespective of study treatment relationship will be provided by SOC and PT.

3.7.2 Laboratory data

When analyzing laboratory data, data from all sources (central and local laboratories) will be combined. The summaries will include all laboratory assessments collected no later than 30 days after the last administration of study treatment or the date of the day prior to the start of open-label ribociclib plus NSAI plus goserelin treatment.

Laboratory data will be classified (by biostatistics/statistical programming) into CTC grades according to the NCI Common Terminology Criteria for Adverse Events (CTCAE) v4.03. The calculation of laboratory CTC grades will be based on the observed laboratory values only; clinical assessments will not be taken into account. The criteria to assign CTC grades in this study are given in Appendix 1.

For laboratory tests where grades are not defined by CTCAE, results will be graded by the low/normal/high classifications based on laboratory normal ranges.

The following summaries will be produced for the laboratory data (by laboratory parameter):

- Number and percentage of patients with each CTC grade as their worst post-baseline value (regardless of the baseline status). Each patient will be counted only for the worst grade observed post baseline.
- Shift tables using CTC grades to compare baseline to the worst post-baseline value will be produced for hematology and biochemistry laboratory parameters with CTC grades.
- For laboratory parameters where CTC grades are not defined, shift tables to the worst post-baseline value will be produced using the low/normal/high classifications based on laboratory reference ranges.

Number and percentage of patients meeting categorical liver function test criteria, including ALT, AST and ALT/AST (>3x, 5x, 8x, 10x, 20x ULN), Total Bilirubin (>1x, 2x ULN), ALP (>1.5x, 2x, 3x, 5x, 8x, 10x ULN), combined categories of ALT/AST and total bilirubin (e.g., ALT/AST>3x UNL & total bilirubin > ULN) as well as Hy's Law criteria (ALT or AST > 3 x ULN and TBIL \geq 2 x ULN and ALP < 2 x ULN). For the combined categories, the assessments need not to be concurrent, i.e., patients are counted based on their most extreme value for each parameter (highest in the case of ALT, AST and TBIL; lowest in the case of ALP). Listing of patients with CTC grade 3 or 4 laboratory abnormalities will be produced and those assessments collected later than 30 days after the last double-blinded study treatment date and before the day of the start of cross-over open-label ribociclib plus NSAID plus goserelin treatment will be flagged in the listing.

Separate listing will be provided for the cross-over analysis set and those assessments collected later than 30 days after the last cross-over open-label study treatment date will be flagged in the listing.

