Increase from baseline grade 0 or 1 to grade 2 (> 3.0 – 5.0 x ULN)	Dose interruption of LEE011/placebo 
 
• If resolved to ≤ baseline grade in ≤ 21 days, then maintain dose level
 
• If resolved to ≤ baseline grade in > 21 days or toxicity recurs, then reduce 1 dose level
 
• Repeat liver enzyme and bilirubin tests twice weekly for 2 weeks after dose resumption
 
• If toxicity recurs after two dose reductions or recovery to ≤ baseline grade is > 28 days, discontinue LEE011/placebo
 

Increase from baseline grade 0 or 1 to grade 3 (> 5.0 – 20.0 x ULN)	Dose interruption of LEE011/placebo until resolved to ≤ baseline grade, then lower 1 dose level of LEE011/placebo 
 
• Repeat liver enzyme and bilirubin tests twice weekly for 2 weeks after dose resumption
 
• If recovery to ≤ baseline grade is > 28 days, discontinue LEE011/placebo
 
• If toxicity recurs, discontinue LEE011/placebo
 

Increase from baseline grade 2 to grade 3 (> 5.0 – 20.0 x ULN)	Dose interruption of LEE011/placebo until resolved to ≤ baseline grade, then lower 1 dose level of LEE011/placebo 
 
• Repeat liver enzyme and bilirubin tests twice weekly for 2 weeks after dose resumption
 
• If toxicity recurs after two dose reductions or recovery to ≤ baseline grade is > 28 days, discontinue LEE011/placebo.
 

Grade 4 (> 20.0 x ULN)	Discontinue LEE011 /placebo
AST or ALT and concurrent Bilirubin	
For patients with normal ALT AND AST AND total bilirubin at baseline: AST or ALT >3.0 x ULN ≥ combined with total bilirubin > 2 x ULN without evidence of cholestasis Or For patient with elevated AST or ALT or total bilirubin at baseline; baseline: [AST or ALT >2 x baseline AND >3.0 x ULN] OR [AST or ALT 8.0 x ULN]- whichever is lower- combined with [total bilirubin > 2x baseline AND >2.0 x ULN]	Discontinue LEE011/placebo
Confounding factors and/or alternative causes for increased transaminases should be excluded before dose interruption/reduction. They include but are not limited to: concomitant medications, herbal preparations or dietary supplements, infection, hepato-biliary disorder or obstruction, new or progressive liver metastasis, and alcohol intake.	

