### 6.3.1.5 Additional follow-up for hepatic toxicities

Increase in transaminases combined with total bilirubin (TBIL) increase may be indicative of drug-induced liver injury (DILI), and should be considered as clinically important events. A study with ribociclib in non-cancer patients with varying degrees of hepatic impairment (mild, moderate, severe based on Child-Pugh classification) matched subjects with normal hepatic function was completed [CLEE011A2109]. Refer to [ribociclib Investigators Brochure] for more details.

The threshold for potential DILI may depend on the patient's baseline AST/ALT and TBIL value; patients meeting any of the following criteria will require further follow-up as outlined below:

- For patients with normal ALT AND AST AND TBIL value at baseline: AST or ALT > 3.0 x ULN combined with TBIL > 2.0 x ULN
- For patients with elevated AST or ALT or TBIL value at baseline: [AST or ALT > 2 x baseline AND > 3.0 x ULN] OR [AST or ALT > 8.0 x ULN], whichever is lower, combined with [TBIL > 2 x baseline AND > 2.0 x ULN]

Medical review needs to ensure that liver test elevations are not caused by cholestasis, defined as: ALP elevation > 2.0 x ULN with R value < 2 in patients without bone metastasis, or elevation of ALP liver fraction in patients with bone metastasis.

Note: The R value is calculated by dividing the ALT by the ALP, using multiples of the ULN for both values [R value = (ALT/ULN)/ (ALP/ULN)]. It denotes the relative pattern of ALT and/or ALP elevation is due to cholestatic or hepatocellular liver injury or mixed type injury

In the absence of cholestasis, these patients must be immediately discontinued from study drug treatment, and repeat LFT testing as soon as possible, preferably within 48 hours from the awareness of the abnormal results. The evaluation should include laboratory tests, detailed history, physical assessment and the possibility of liver metastasis or new liver lesions, obstructions/compressions, etc.

Hepatic toxicity monitoring includes assessment of the following LFTs: albumin, ALT, AST, total bilirubin, direct and indirect bilirubin, alkaline phosphatase (fractionated if alkaline phosphatase is grade 2 or higher), creatinine kinase, prothrombin time (PT)/INR and GGT. For patients with Gilbert Syndrome: total and direct bilirubin must be monitored, intensified monitoring applies to changes in direct bilirubin only.

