2.1.8 On-treatment assessment/event

Safety summaries and selected summaries of deaths will summarize only on-treatment assessments/events.

Double-blind on-treatment period:

An on-treatment assessment/event is defined as any assessment/event in the following time interval:

[date of first administration of study treatment, the earliest between the date of last administration of study treatment + 30 days and the date of first administration of cross-over open-label ribociclib plus NSAID plus goserelin treatment – 1 day], i.e., including the lower and upper limits.

The double-blind on-treatment period is the **default** on-treatment period used in the analyses unless specified otherwise.

Cross-over on-treatment period:

An on-treatment assessment/event is defined as any assessment/event in the following time interval: [date of first administration of the cross-over open-label ribociclib plus NSAID plus goserelin treatment, date of last administration of the cross-over open-label ribociclib plus NSAID plus goserelin treatment + 30 days], i.e., including the lower and upper limits.

(Note: However, the calculation of study treatment duration will use different rules as specified in [Section 3.5.1](#)).

An AE started in the screening phase and ongoing in the on-treatment phase will not be considered as an on-treatment AE unless it has worsened.

If the last date of study treatment is missing, any assessment/event occurring after the start of study treatment will be considered as on-treatment.

Data listings will include all assessments/events, flagging those which are not on-treatment.

Note: The date of first administration of study treatment and the date of last administration of study treatment are defined in [Sections 2.1.4](#) and [2.1.5](#), respectively.

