3.9.2 Laboratory data

On analyzing laboratory data, data from all sources (central and local laboratories) will be combined. The summaries will include all laboratory assessments collected no later than 30 days after the last administration of study treatment. All laboratory assessments will be listed and those collected later than 30 days after the last treatment date will be flagged in the listings.

Laboratory data will be classified (by biostatistics/statistical reporting) into CTC grades according to the NCI CTCAE v4.0.3. The calculation of laboratory CTC grades will be based on the observed laboratory values only; clinical assessments will not be taken into account. The criteria to assign CTC grades are given in Appendix 1.

For laboratory tests where grades are not defined by CTCAE, results will be graded by the low/normal/high classifications based on laboratory normal ranges.

The following summaries will be produced for the laboratory data (by laboratory parameter):

- Number and percentage of patients with each CTC grade as their worst post-baseline value (regardless of the baseline status). Each patient will be counted only for the worst grade observed post baseline.
- Shift tables using CTC grades to compare baseline to the worst post-baseline value will be produced for hematology and biochemistry laboratory parameters with CTC grades.

- For laboratory parameters where CTC grades are not defined, shift tables to the worst post-baseline value will be produced using the low/normal/high classifications based on laboratory reference ranges.
- Number and percentage of patients meeting categorical liver function test criteria, including ALT, AST and ALT/AST (>3x, 5x, 8x, 10x, 20x ULN), Total Bilirubin (>1x, 2x ULN), ALP (>1.5x, 2x, 3x, 5x, 8x, 10x ULN), combined categories of ALT/AST and total bilirubin (e.g., ALT/AST>3x ULN & total bilirubin > ULN) as well as potential Hy's Law criteria (ALT or AST > 3 x ULN and TBIL > 2 x ULN and ALP < 2 x ULN). For the combined categories, the assessments need not be concurrent, i.e. patients are counted based on their most extreme value for each parameter (highest in the case of ALT, AST and TBIL; lowest in the case of ALP).
- Box plots of laboratory values by scheduled time point and treatment arm.

The following listings will be produced for the laboratory data:

- Listing of patients with CTC grade 3 or 4 laboratory abnormalities;

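### The final SAP's Hy's Law count is a non-concurrent screen (highest ALT/AST and bilirubin, lowest ALP), reported with no concurrent count beside it

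*SAP*

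**What the plan says.** The final SAP (section 3.7.2) plans a table of liver-test categories that ends "as well as Hy's Law criteria (ALT or AST > 3 x ULN and TBIL" at or above 2 x ULN, with ALP below 2 x ULN. Where a category draws on several parameters, "the assessments need not to be concurrent, i.e., patients are counted based on their most extreme value for each parameter". The section then takes the maximum of ALT, AST and bilirubin but the minimum of ALP. ALP enters a combined category only through the Hy's Law row, so the lowest-value rule is written for that row.

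The values are bounded in time. Section 3.7.2 takes laboratory data "collected no later than 30 days after the last administration of study treatment or the date of the day prior to the start of open-label" cross-over treatment. Section 2.1.8 sets the default on-treatment window to end at "the earliest between the date of last administration of study treatment + 30 days and the date of first administration of cross-over" treatment, less one day.

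The primary-analysis SAP (section 3.9.2) has the same timing rule, including "lowest in the case of ALP". It calls the criteria potential Hy's Law and sets bilirubin above, not at or above, 2 x ULN.

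The protocol defines the signal differently. The relevant block of Table 6-4 is headed "AST or ALT and concurrent Bilirubin". Section 6.3.1.5 adds: "Medical review needs to ensure that liver test elevations are not caused by cholestasis". There, cholestasis means ALP above 2 x ULN with an R value below 2 in patients without bone metastasis, or a raised ALP liver fraction in patients with bone metastasis.

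**The concern.** The ALP limb is meant to separate hepatocellular injury from cholestasis. That works only if ALP is read at the time of the transaminase and bilirubin rise. Read at its lowest, one value below 2 x ULN anywhere in the window satisfies it. Separately, the highest ALT and the highest bilirubin may come from different episodes.

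Protocol section 1.4.1.1 names hepatobiliary toxicity as an important identified risk. It reports four patients (1.2%) meeting biochemical and clinical Hy's Law criteria in the ribociclib arm of the letrozole trial in postmenopausal women. With counts that small, one or two extra patients change what a safety reader sees. The final SAP has dropped the qualifier that marked the row as a screen.

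**Working it through.** The documents state no result for this table, so there is no figure to reproduce. The check applies the rule literally, in multiples of ULN.

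**1. The rule.** A patient counts if max(ALT or AST) > 3 and max(TBIL) ≥ 2 and min(ALP) < 2, each taken over her on-treatment samples.

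**2. When the ALP condition removes someone.** Only if all n of her ALP values are ≥ 2. If each is ≥ 2 independently with probability p (assumed), that probability is p^n:
- p = 0.5: 0.5^4 = 6.3%; 0.5^8 = 0.4%
- p = 0.9: 0.9^8 = 43%; 0.9^20 = 12%

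The condition is weak when ALP varies, but it still acts when ALP stays high.

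**3. Two constructed patients.**
- *Unrelated events.* Day 15: ALT 4, TBIL 0.6, ALP 1.0. Day 400: ALT 1.0, TBIL 0.6, ALP 0.9. Day 1100: ALT 1.2, TBIL 2.5, ALP 4.0. The extremes are 4, 2.5 and 0.9, so she counts. No single sample meets the criteria.
- *One cholestatic episode.* Day 15: ALT 1.0, TBIL 0.6, ALP 1.0. Day 400: ALT 6, TBIL 3, ALP 5. The extremes are 6, 3 and 1.0, so she counts. At the episode R = 6/5 = 1.2, which with ALP above 2 is cholestasis under protocol 6.3.1.5 if she has no bone metastasis.

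**4. Are such gaps possible on treatment?** Yes, for long-treated patients. Enrolment ended on 01-Aug-2016, and the Amendment 7 rationale reports 114 patients still on treatment on 08-Jan-2020. They had been randomized at least 1255 days (1255/30.4375 = 41 months) earlier.

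**5. Direction.** If one sample meets all three conditions, the highest ALT/AST and TBIL and the lowest ALP meet them too. The SAP count therefore contains every same-sample case and can only exceed that count. The excess grows with the number of samples. Of the 114, 79 were in the ribociclib arm and 35 in the placebo arm, and placebo windows also end at cross-over. Any excess is therefore probably larger in the ribociclib arm.

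**6. Size, on assumed rates only.** With 672 randomized 1:1 there are about 336 per arm. Expected chance pairings = 336 × P(ALT/AST > 3) × P(TBIL ≥ 2), taking the two as independent:
- 336 × 0.08 × 0.01 = 0.3
- 336 × 0.08 × 0.02 = 0.5
- 336 × 0.16 × 0.04 = 2.2
- 336 × 0.15 × 0.05 = 2.5

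Built up by visit, with assumed rates of 1% and 0.15% per sample, the formula is 336 × (1 − 0.99^n)(1 − 0.9985^n). It gives 0.31 for n = 8, 0.80 for n = 13 and 1.81 for n = 20. Requiring all three conditions in one sample, 336 × n × 0.01 × 0.0015 × P(ALP < 2) with P(ALP < 2) between 0.80 and 0.95, gives 0.03 to 0.10. Cholestatic single episodes, as in the second patient, would come on top and cannot be sized.

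**7. Can the planned laboratory listing separate the cases?** Section 3.7.2 specifies a listing of grade 3 or 4 values. By SAP Appendix 1, ALT/AST above 3 to 5 x ULN and bilirubin above 1.5 to 3 x ULN are grade 2. A patient with ALT 4 and TBIL 2.5 would not appear. The primary-analysis SAP and protocol section 10.5.3.3 both planned a listing of all laboratory data.

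**The case against.** The strongest reply is that this is a deliberate and disclosed screen. The primary-analysis SAP's change history records the non-concurrent rule as a clarification, and for a rare signal a rule that leans towards sensitivity is defensible. Case-level judgement sits elsewhere: section 6.3.1.5 requires medical review for cholestasis, and confirmed cases with no other cause are reported as SAEs, which the SAP tabulates. All of this stands. It supports keeping the row. It does not support presenting the row as Hy's Law criteria with no concurrent count.

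A reader might infer that the ALP condition does nothing, or that cholestasis can never be excluded. The rule does not say that: a patient whose ALP stays at or above 2 x ULN throughout is still removed. A reader might also suppose that values from the whole of follow-up are pooled. They are confined to the on-treatment window.

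Nor would a plain same-sample ALP cut-off reproduce the protocol's definition. With ALT 10, TBIL 3 and ALP 3, R is 3.3, which is not cholestatic by the R criterion, yet an ALP < 2 rule drops her. If all her ALP values are that high, for example from bone disease, the SAP's own screen drops her as well. So the claim that the screen over-counts holds against the same three conditions within a sample, not against the protocol's clinical definition.

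**Conclusion.** The point holds as a reporting defect in the final SAP. The row labelled Hy's Law criteria is a non-concurrent screen. It does not match the protocol's concurrent, non-cholestatic definition, and the laboratory section plans no count or listing from which the two could be reconciled.

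The direction relative to a same-sample count is certain. The imbalance between arms is probable, because it rests on longer treatment and more samples in the ribociclib arm. The size cannot be derived from the documents: 0.3 to 2.5 chance pairings per 336 patients depends on assumed rates and on independence. One might infer that spurious cases would rival the four reported in the other trial. Only the upper end of the assumed range comes near that, and nothing in the documents fixes the rates.

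The efficacy conclusions are untouched. The difference between bilirubin at or above 2 x ULN and above 2 x ULN matters only for values exactly at the limit, but one definition should apply throughout.

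**What to change.** 1. Relabel the existing row as *potential Hy's Law, non-concurrent screen*.
2. Add a row requiring ALT or AST > 3 x ULN and the bilirubin threshold in the same sample or within a short window stated in advance. Show it twice: without an ALP condition, and with ALP < 2 x ULN taken from that same sample or window.
3. List every patient counted in any of these rows, with dated ALT, AST, bilirubin and ALP, the R value, and bone and liver metastasis status, so that cholestasis can be judged as in protocol 6.3.1.5.
4. Reconcile the bilirubin cut-off between final SAP 3.7.2 (at or above 2 x ULN) and primary-analysis SAP 3.9.2, protocol Table 6-4 and protocol 6.3.1.5 (above 2 x ULN).

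The cost is one extra derivation and one listing from laboratory data already collected. The row with same-sample ALP may miss injury in patients whose ALP is raised by bone disease, which the row without the ALP condition covers. Cases with widely spaced samples may miss the concurrent rows, which the retained screen covers.
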